6.5.6. Concomitant Medications and Non-Drug Treatments

Concomitant medications taken during the study treatment period will be summarized for all patients in the AT population. Concomitant medications refer to all medications which started prior to first dose of study treatment and continued during the treatment-emergent period (earliest of 30 days after the last dose of study drug treatment, the start of cytotoxic chemotherapy, the start of a lutamide (bicalutamide, nilutamide, or flutamide), or the start of a new investigational therapy (whichever occurs first)) as well as those started during the ontreatment period.

Concomitant medications will be coded in the WHO Drug coding dictionary and will be tabulated by Anatomical Therapeutic Chemical (ATC) Classification level 2 and preferred term in descending order of frequency. In case of equal frequency regarding drug class (respectively drug name), alphabetical order will be used. A patient will be counted only

once within a given drug class and within a given drug name, even if he/she received the same medication at different times. Preferred Terms will be reported under each ATC class that it is included under within WHO Drug (no primary path is available in WHO Drug).

All concomitant medications and non-drug treatments recorded on the case report form will also be listed.

6.6. Safety Summaries and Analyses

All patients in the AT population will be used in the safety analyses.

6.6.1. Adverse Events

Adverse events will be coded using MedDRA, in accordance with the version(s) documented in the data management plan. Adverse events will be graded by the investigator using the CTCAE v4.0.

[figure not shown]
All analyses will be based on treatment emergent events unless otherwise specified. Treatment emergent is defined in Section 3.5. AEs not considered treatment emergent will be flagged in data listings. Only TEAEs with onset date to the earliest of 30 days after the last dose of study drug treatment, the start of cytotoxic chemotherapy, the start of a lutamide (bicalutamide, nilutamide, or flutamide), or the start of a new investigational therapy (whichever occurs first) will be included in the adverse event summaries.

Adverse event incidence will be summarized with frequency and percentage using MedDRA. Some summaries are by system organ class (SOC) and preferred term (PT), while others are only by PT (see below). In addition, adverse event incidence will also be summarized by severity and relationship to study drug. The denominator for the adverse event incidence will be based on the number of patients in the AT population unless otherwise specified.

Patients with multiple occurrences of events for a given preferred term (even if concurrent), system organ class, or overall will only be counted once at the worst severity and strongest relationship to study drug for each preferred term, system organ class, and overall, respectively. If relationship to study drug is missing, the adverse event will be counted as treatment-related. Adverse event listings will show missing relationship as missing.

Tabular summaries including numbers and percentages of the following adverse events will be provided:

- TEAEs;
- TEAEs by SOC and PT;
- TEAEs by PT and maximum severity;
- TEAEs (treatment related);
- TEAEs (treatment related) by SOC and PT;

- TEAEs (treatment related) by PT and maximum severity;
- TEAEs leading to study drug discontinuation by PT;
- TEAEs leading to temporary study drug interruptions by PT;
- TEAEs leading to dose interruptions or reductions by PT;
- Serious TEAEs;
- Serious TEAEs by SOC, PT and maximum severity.

6.6.2. Adverse Events of Special Interest

Not applicable.

6.6.3. Deaths

The frequency (number and percentage) of patients in the AT population who died and who also died within 30 days after last dose of study treatment as well as the primary reason for death will be tabulated.

Date and cause of death will be provided in individual patient data listing together with selected dosing information (date of first/last administration, dose).

[figure not shown]
6.6.4. Laboratory Data

Laboratory data in this study consist of hematology values and chemistry tests. Only data collected from the central laboratory during the treatment-emergent period will be summarized. Laboratory data collected outside the treatment-emergent period will only be listed in the data listings.

Laboratory results will be converted to International System of Units (SI) units which will be used for applying toxicity grades and for all summaries.

Quantitative data will be summarized using simple descriptive statistics (mean, standard deviation, median, quartiles, minimum, and maximum) of actual values and change from baseline for each nominal visit over time (ie, unscheduled assessments will be excluded). The total number of patients for change from baseline will include all patients in the treatment arm who have both a baseline and a value at the nominal visit.

As described in Section 3.4, baseline will defined as the last assessment performed on or prior to date of the first dose of study treatment. If there are multiple assessments that meet the baseline definition on the same day without the ability to determine which was truly last, then the worst grade will be assigned as the baseline grade.

Results collected as strict inequalities (eg, >10, <10) will be converted to numeric values by subtracting a factor of <0.001>. Expressions of the form" \geq " or " \leq " will be converted to the end point. These numeric values will be evaluated for clinically significant abnormalities, but will not be included in calculations of summary statistics.

Additionally, laboratory results will be programmatically classified according to NCI-CTCAE version 4.0 grade. Non-numerical qualifiers will not be taken into consideration in the derivation of grade (eg, hypokalemia Grade 1 and Grade 2 are only distinguished by a non-numerical qualifier and therefore Grade 2 will not be derived). In summary statistics the number and percentage of patients corresponding to grades that only include non-quantitative criteria will be displayed as a blank or NA (not assessed) rather than 0. If there is any overlap between grade criteria (eg, CTCAE grading criteria for Creatinine Increased – a value can fall into one range based on comparison to ULN and another range based on comparison to baseline), the highest (worst) grade would be assigned to that record. Grade 5 is defined in the CTCAE criteria guidance as an event with an outcome of death. Since laboratory data does not collect an outcome, Grade 5 is not used when programmatically grading laboratory data. Grade 0 or Outside Toxicity Reference (OTR) is not defined specifically by in the CTCAE guidance. However, programmatically this is used as a category to represent those patients who did not meet any of the Grades 1 to 4 criteria. If the laboratory value is evaluable for CTCAE criteria grading (numeric value is present, valid units and ranges are present as required to allow conversion to standard units and grading), and does not qualify for any of the Grade 1-4 criteria for a given lab test, then the value is assigned as Grade 0 or OTR.

Normal ranges will be implemented to identify values that are outside the normal ranges and create the NCI toxicity grade using the CTCAE version 4.0. Parameters that have criteria available for both low and high values will be summarized for both criteria (low and high). Patients will only be counted once for each criterion. The same patient can be counted for both criteria if the patient has laboratory values meeting each criterion. The change from baseline to post baseline value will be calculated for each laboratory parameter where available.

For laboratory parameters that are gradable by the CTCAE, a shift table will be provided for each parameter to summarize baseline toxicity grade versus worst post baseline toxicity grade during the treatment-emergent period. The number and percentage of patients will be provided for each parameter.

For each laboratory parameter that is not able to be graded by the CTCAE, a shift table based on the normal range (low, normal, and high) will be provided to summarize the baseline result versus both the lowest and the highest post baseline result during the treatment-emergent period.

For patients with grade 3 and/or grade 4 laboratory values in the treatment-emergent period, a by-patient data listing will be presented to display data including visit label, assessment date (day), laboratory value, and normal range flag (low, normal, and high). The baseline value will be flagged in this data listing.

Protocol MDV3100-18 (C3431012) (Enzalutamide) Statistical Analysis Plan

The number and proportion of patients with liver function test elevations will be presented. Liver function test elevations are assessed by using post baseline results in ALT, AST, and total bilirubin during the treatment-emergent period based upon the definitions presented below:

Categories of Liver Function Test Elevations

| Parameter | Elevation |
|-----------------|-----------|
| | |
| AST | >5 x ULN |
| ALT | >5 x ULN |
| Total bilirubin | >5 x ULN |

ALT, alanine aminotransferase; AST, aspartate aminotransferase; ULN, upper limit of normal

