10.6 Determination of Sample Size

The total number of patients to be included in this study is approximately 20 and is based on practical clinical considerations.

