5.3. Methods to Manage Missing Data

Missing data will not be imputed unless specified elsewhere in the SAP. Missing dates or partially missing dates will be imputed conservatively for adverse events and prior/concomitant medications/procedures. Specific rules for handling missing or partially missing dates for date of birth, adverse events, prior/concomitant medications/procedures, and diagnosis of cancer are provided in Appendix 1. Imputation of Missing/Partially Missing Dates. Any imputations will occur at the analysis dataset level and not the raw dataset level. Additionally, in all patient data listings imputed values will be presented and flagged as imputed.

Missing statistics, eg, when they cannot be calculated, should be presented as 'ND' for not done, 'NR' for not reached or 'NA' for not applicable. For example, if N=1, the measure of variability cannot be computed and should be presented as 'ND' or 'NA'. If too few events are observed in the KM analyses, then certain quartiles may not be estimable; hence NR should be presented.

Missing toxicity grades for adverse events:

Prior to Study Treatment: If no toxicity grade is available or the grade is reported as unknown for an adverse event prior to the first study treatment, then Grade 1 will be assumed for purposes of defining a baseline grade for assessing if further occurrences are treatment emergent. However, if the patient experiences multiple episodes of the same AE prior to study treatment, then the maximum toxicity grade observed prior to study treatment will be utilized in assessing if further occurrences are treatment emergent.

During Study Treatment: If no toxicity grade is available or the grade is reported as unknown for an adverse event during the study treatment, then the event will be considered treatment emergent unless a baseline event was reported as Grade 4.

In summaries which present maximum toxicity grade, the maximum of non-missing grades will be displayed. Missing grade will only be displayed for cases where a patient reported only one event and the grade is missing.

For incomplete day of last dose of study drug, the 15th of the month will be assumed in determining the treatment-emergent period.

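### SAP 6.6.4 leaves laboratory results reported as inequalities out of the by-visit summaries, which biases those summaries wherever such results occur

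*SAP*

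**What the plan says.** SAP section 6.6.4 sets out the by-visit laboratory summary: "Quantitative data will be summarized using simple descriptive statistics (mean, standard deviation, median, quartiles, minimum, and maximum"), for actual values and for change from baseline at each nominal visit. On the denominator for a given visit it says: "The total number of patients for change from baseline will include all patients in the treatment arm who have both a baseline and a value". It does not say whether a result reported as an inequality counts as a value.

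The same section then deals with inequalities: "Results collected as strict inequalities (eg, >10, <10) will be converted to numeric values by subtracting a factor of <0.001>". Non-strict inequalities are set to the end point. Of all these converted results it says: "These numeric values will be evaluated for clinically significant abnormalities, but will not be included in calculations of summary statistics".

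Nothing elsewhere restores or counts the excluded results. SAP section 5.3 gives the general position: "Missing data will not be imputed unless specified elsewhere in the SAP".

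Other laboratory outputs in 6.6.4 are not named in the exclusion. For gradable parameters, "a shift table will be provided for each parameter to summarize baseline toxicity grade versus worst post baseline toxicity grade". Parameters that cannot be graded get a low/normal/high shift table using both the lowest and the highest post-baseline result. Liver-test elevations are counted. There is also a listing: "For patients with grade 3 and/or grade 4 laboratory values in the treatment-emergent period, a by-patient data listing will be presented".

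**The concern.** A result below a lower limit is known to be low, and a result above an upper limit is known to be high. Removing it from a summary is selection on the outcome, and the values left are not a random subset. Where the limited results lie on one side, the mean and median move away from that side and the spread narrows.

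Order statistics do not need the exclusion. A value beyond a limit still has a known rank, unless laboratories use different limits or the statistic itself falls within the limited part.

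Change from baseline is affected too. A patient whose result crosses a limit drops out of that calculation at the visit where the change may be largest. The n contributing can then vary between visits for a reason that the table does not show. What is at stake is the accuracy of the descriptive safety tables, not an endpoint or a decision.

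**Working it through.** The plan states no figure on this point, so there is nothing to reproduce. The calculation below is an illustration.

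**Inputs**
- The rule and the statistics it touches: SAP 6.6.4.
- Number of patients: "The total number of patients to be included in this study is approximately 20" (Protocol 10.6).
- Share q of results that are limited: not in the documents; assumed 1% to 20%, on one side.
- Spread: not in the documents; assumed log-normal with log-SD s of 0.3 to 0.5, and 0.05 to 0.1 for a narrow analyte.

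**Step 1. Lower limit.** Let X = exp(sZ), with Z standard normal and z_q its q-quantile. Relative to the true value:
- median after exclusion = exp(s × z((1+q)/2))
- mean after exclusion = P(Z > z_q − s)/(1 − q)
- mean with values kept at the limit = P(Z > z_q − s) + q × exp(s × z_q − s²/2); the median is then unchanged while q is below 50%

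Example with q = 0.05, s = 0.3:
- Median: exp(0.3 × 0.0627) = 1.019.
- Mean after exclusion: P(Z > −1.945)/0.95 = 0.9741/0.95 = 1.025.
- Mean kept at the limit: 0.9741 + 0.05 × exp(−0.4935 − 0.045) = 1.003.

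| Limited | Median, excluded | Mean, excluded | Mean, kept at limit |
|---|---|---|---|
| 1% | +0.4% to +0.6% | +0.6% to +0.8% | under +0.1% |
| 5% | +1.9% to +3.2% | +2.5% to +3.6% | +0.3% |
| 10% | +3.8% to +6.5% | +4.8% to +7.0% | +0.8% to +0.9% |
| 20% | +7.9% to +13.5% | +9.1% to +13.8% | +2.2% to +2.6% |

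With s = 0.05 to 0.1 and 5% limited, the median moves 0.3% to 0.6% and the mean 0.5% to 1.0%.

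**Step 2. Upper limit.** The direction reverses.
- Median after exclusion = exp(s × z((1−q)/2)): −1.9% to −3.1% at 5% limited.
- Mean after exclusion = P(Z < z_(1−q) − s)/(1 − q): −4.1% to −8.0% at 5%.
- Mean kept at the limit = P(Z < z_(1−q) − s) + q × exp(s × z_(1−q) − s²/2): −1.1% to −2.6% at 5%, and roughly −5% to −10% at 20%.

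Keeping values at the limit is less biased, but the mean is still only approximate when many results in a long upper tail are limited.

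**Step 3. Spread and extremes.** On a normal scale with fraction f removed below c = z(f), the SD after exclusion is √(1 + c·φ(c)/(1−f) − (φ(c)/(1−f))²). This gives 0.97, 0.90 and 0.76 of the true SD at 1%, 5% and 20%. In 200,000 simulated samples of 20, the expected minimum is −1.87 SD. It becomes −1.41 after dropping the lowest result and −1.13 after dropping the lowest two. The chance that at least one of 20 results is limited is 1 − (1−q)^20, which is 18%, 64% and 88% at q = 1%, 5% and 10%.

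**Step 4. The conversion.** Subtracting 0.001 in both directions gives 10 − 0.001 = 9.999 for '>10' and also for '<10'. An upper-limited result is therefore placed below its limit, below a measured 10, and level with a lower-limited one. This matters now for the abnormality evaluation. It would also matter for ranks if the converted values were simply put back into the summaries.

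**The case against.** The case for leaving the rule alone has several sound parts.

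- **Extreme results are still reported.** The exclusion sentence keeps these values for abnormality evaluation, and the graded and ungraded shift tables, the liver-test counts and the grade 3/4 listing are separate outputs. A reader might infer that a safety signal is lost; the documents do not support that.
- **Tables can disagree for other reasons.** A reader might infer that a by-visit maximum lower than a graded 3 or 4 result must come from this rule. By-visit summaries also omit unscheduled assessments (SAP 6.6.4), which worst-case safety analyses use (SAP 5.2.4), and windowing keeps the observation closest to the target day (SAP Appendix 3). The fix would not remove those mismatches.
- **The size is hypothetical.** No document says that any result is reported as an inequality. Many analytes in Protocol Table 12, such as the electrolytes, may have few or none, and a narrow spread makes the shift small.
- **Substituting the limit is single imputation.** It leaves some bias in the mean and SD. Prespecified exclusion from a descriptive table of about 20 patients, in a study with no formal hypothesis (SAP 5.1), can be defended.
- **A prior conflict exists.** SAP 6.6.4 summarises only central-laboratory data, while Protocol sections 8.4 and 12 have the safety samples analysed locally. Read literally, there would be no summary to bias. That needs its own correction. This point assumes that the local results are the ones meant.

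These arguments limit how much the point matters. They do not remove the dependence of the exclusion on the value, or explain why no count of excluded results is required.

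**Conclusion.** The point stands as a low-severity one. Where inequality results occur on one side, the by-visit laboratory summaries lean towards the reportable range, the SD is too small, the minimum or maximum can omit the most extreme result, and patients who cross a limit leave the change-from-baseline summary. Two-sided limiting could leave the mean and median nearly right but would still affect the extremes.

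The size rests wholly on assumed inputs. For lower limits and log-SD 0.3 to 0.5, the median shift runs from about half a percent at 1% limited to 8% to 14% at 20%. It is zero for analytes with no such results. The primary and secondary endpoints are untouched.

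It is tempting to say that the reported minimum or maximum is wrong whenever one limited result occurs. That goes too far. Tests are run at local laboratories (Protocol 8.4), limits may differ between them, and a '<5' from one site need not be the minimum if another site reports 3.

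**What to change.** In SAP 6.6.4, replace the exclusion with wording such as: *For summary statistics, results reported as inequalities are included at the reporting limit itself (not the limit minus 0.001), in n, mean, SD, median, quartiles, minimum, maximum and change from baseline; a minimum or maximum that is such a value is shown with its inequality sign; and the number of such values is shown per parameter and visit.*

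Separately, correct the conversion used for abnormality evaluation so that '>' results are not placed below their limit.

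The cost is a short SAP edit and a small programming change. The downside is also small. The mean and SD are approximate where many values are limited, and ranks can be ambiguous if local laboratories use different limits, so the median should be read alongside the count. If the sponsor prefers to keep the exclusion, the count of excluded results per parameter and visit should still be shown.

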4.2 Exclusion Criteria

Each patient eligible to participate in this study must NOT meet any of the following exclusion criteria:

1. Prior enzalutamide, abiraterone acetate, aminoglutethimide, ketoconazole, radium Ra 223 dichloride or other bone-targeting radionuclides, or cytotoxic chemotherapy in the CRPC setting for the treatment of prostate cancer or participation in a clinical trial of an investigational agent that inhibits the androgen receptor or androgen synthesis (unless treatment was placebo).
2. Treatment with hormonal therapy (eg, androgen receptor inhibitors, 5-alpha reductase inhibitors) or biologic therapy for prostate cancer (other than LHRH analogue therapy) within 4 weeks before day 1.
3. Initiation of new treatment with denosumab, bisphosphonates, or systemic corticosteroids for treatment of prostate cancer within 4 weeks before day 1.
4. Use of an investigational agent within 4 weeks before the screening visit.
5. Radiation therapy to bone within 4 weeks before day 1.
6. Use of opiate analgesics for prostate cancer pain within 4 weeks before day 1.
7. History of another invasive cancer within 3 years before screening, with the exception of fully treated cancers with a remote probability of recurrence. The medical monitor and investigator must agree that the possibility of recurrence is remote for exceptions.
8. Screening ^{99m}Tc-MDP bone scintigraphy showing a superscan.
9. Visceral (eg, lung, liver) metastatic disease (biopsy not necessary). Adenopathy is allowed.
10. Absolute neutrophil count < 1500/ μ L, platelet count < 100,000/ μ L, or hemoglobin < 6.2 mmol/L (< 10 g/dL) at screening. Patients may not have received growth factors or blood transfusions within 7 days, inclusive, before obtaining the screening hematology values.
11. Total bilirubin \geq 1.5 times the upper limit of normal (ULN) (except patients with a diagnosis of Gilbert's disease), or alanine aminotransferase (ALT) or aspartate aminotransferase (AST) \geq 2.5 times ULN at screening.
12. Creatinine > 177 μ mol/L (> 2 mg/dL) at screening.
13. Albumin < 30 g/L (< 3.0 g/dL) at screening.
14. Current or previously treated brain metastasis or active leptomeningeal disease.
15. History of seizure any time in the past for any reason or any condition that may predispose to seizures.
16. History of loss of consciousness or transient ischemic attack within 12 months before screening.

17. Clinically significant cardiovascular disease, including the following:

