5.3 Permanent Treatment Discontinuation

Permanent treatment discontinuation is defined as cessation of study drug treatment administration. Safety follow-up will be performed per [Section 5.4](#).

Temporary treatment interruption is not considered permanent discontinuation. Regularly scheduled study visits will continue for patients based on their enrollment date when their treatment is interrupted any time and restarted.

The reasons that require patients to *permanently discontinue* study drug treatment are as follows:

- Adverse event or intercurrent illness: Any intolerable adverse event that cannot be ameliorated by the use of adequate medical intervention or that in the opinion of the investigator or medical monitor would lead to undue risk if study treatment were continued. Refer to [Section 8.3.1](#).
- Gross noncompliance with protocol: The medical monitor or investigator may request permanent treatment discontinuation in the event of a major protocol deviation, lack of cooperation, or noncompliance.
- Administration of prohibited concomitant therapy: Refer to [Section 7.2](#). NOTE: Patients who discontinue due to administration of a prohibited concomitant therapy will remain in the study and complete safety follow-up assessments per [Section 5.4](#).
- Laboratory abnormality defined as follows, unless the cause is identified and satisfactorily addressed, and the abnormality subsequently improves:
 - Creatinine > 354 µmol/L (> 4.0 mg/dL)
 - AST, ALT, or total bilirubin > 5-times the ULN
 - Absolute neutrophil count ≤ 750/µL
 - Platelet count < 50,000/µL
- Seizure: Regardless of resolution of any identified etiology.
- Death

- Loss to follow-up: Refer to [Section 5.5](#).
- Sponsor discontinuation of study: The sponsor reserves the right to terminate the study any time for any reason as described in [Section 13.6](#). The sponsor will terminate this study following completion of the study objectives, or earlier if deemed necessary.

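### The SAP liver table counts AST, ALT and total bilirubin one at a time and only above 5 x ULN, and no planned summary shows whether transaminase and bilirubin rose together in the same patient (minor, reporting only)

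*SAP*

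**What the plan says.** SAP Section 6.6.4 promises a liver display: "The number and proportion of patients with liver function test elevations will be presented". Its inputs are defined next: "Liver function test elevations are assessed by using post baseline results in ALT, AST, and total bilirubin during the treatment-emergent period". The category table has one row each for AST, ALT and total bilirubin, all with the same strict inequality; the last reads "Total bilirubin | >5 x ULN". It has no lower category and no combined category.

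Protocol Section 5.3 lists "AST, ALT, or total bilirubin > 5-times the ULN" among the laboratory abnormalities that call for permanent discontinuation, with the qualifier "unless the cause is identified and satisfactorily addressed, and the abnormality subsequently improves". Exclusion criterion 11 in Protocol Section 4.2 sets the entry ceilings. Men with ALT or AST at or above "2.5 times ULN at screening" are excluded, as are men with bilirubin at or above 1.5 x ULN unless they have Gilbert's disease.

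Other displays in SAP Section 6.6.4 also cover liver tests:
- For CTCAE-gradable parameters, "a shift table will be provided for each parameter to summarize baseline toxicity grade versus worst post baseline toxicity grade during the treatment-emergent period".
- Descriptive statistics by nominal visit, including the maximum and the change from baseline.
- A by-patient listing, with dates, values and normal-range flags, for patients with any grade 3 or 4 laboratory value.

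SAP Section 6.6.2 (adverse events of special interest) is marked not applicable.

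On the data source, SAP Section 6.6.4 summarises only central-laboratory results. Protocol Sections 8.4 and 12, and the schedule in Protocol Appendix 2, have haematology and chemistry done at local laboratories.

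**The concern.** The only display devoted to liver tests starts at the figure the protocol uses as a discontinuation limit, and it treats the three tests as unrelated. A man can enter below the ceilings of 2.5 x ULN (ALT, AST) and 1.5 x ULN (bilirubin), rise to exactly 5 x ULN on all three tests in one sample, and fall in no row. Above the limit, one man counted in both the ALT row and the bilirubin row looks the same as two men counted once each.

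Whether the two kinds of elevation coincide in one patient is a natural question for a safety reviewer, and marginal counts cannot answer it. At stake is the completeness of the safety summary. If no joint category is fixed in advance, someone who wants one will have to choose cut-offs after seeing the data.

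**Working it through.** The plan gives no figure to reproduce. The check runs example patients through the table, asks what the other displays would show, and then sizes one case.

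**1. The table as a rule.** A patient is counted in a row if that test exceeds 5 x ULN at any post-baseline time in the treatment-emergent period. The values below are illustrative multiples of ULN, not data.

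| AST | ALT | Bilirubin | Rows entered |
|---|---|---|---|
| 1 | 3.5 | 2.5 | none |
| 4 | 4 | 2.1 | none |
| 4.9 | 4.9 | 4.9 | none |
| 5 | 5 | 5 | none (strict inequality) |
| 1 | 5.1 | 2.5 | ALT only |
| 6 | 6 | 6 | all three |

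Any joint elevation with every value at or below 5 x ULN enters no row. Where only one value exceeds 5 x ULN, the other elevation is not shown.

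**2. The single-parameter displays.** Take two men, all baselines at 1 x ULN, measured at the same visit.

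- Case A: man 1 has ALT 4 and bilirubin 2.1; man 2 has 1 and 1.
- Case B: man 1 has ALT 4 and bilirubin 1; man 2 has ALT 1 and bilirubin 2.1.

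In both cases the ALT values are {4, 1} and the bilirubin values are {2.1, 1}. The shift tables, by-visit statistics and liver table are therefore identical in A and B. Both elevations are reported in the shift tables to the extent that they are graded, but nothing in these summaries tells a joint elevation in one man from single elevations in two.

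**3. The grade 3/4 listing.** This listing is by patient and dated, so it can show coincidence once a patient qualifies. It includes a normal flag and the baseline value, which suggests that it is not confined to the grade 3 or 4 results. A single test triggers it, so a patient with two lower-grade elevations does not qualify through them. The documents do not reproduce the CTCAE cut-offs, so whether the 4.9/4.9/4.9 patient qualifies cannot be settled from them.

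**4. Size of one case.** With n = 20 and exact two-sided 95% limits:

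- 0/20: the upper limit is 1 − 0.025^(1/20) = 0.168, giving 0% to 16.8%.
- 1/20 = 5.0%: the lower limit is 1 − 0.975^(1/20) = 0.001; the upper limit solves (1 − p)^20 + 20p(1 − p)^19 = 0.025, so p = 0.249. The interval is 0.1% to 24.9%.

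**5. Source of the data.** The SAP restricts summaries to central-laboratory values, while the protocol has every safety chemistry test done locally. Read literally, the liver table could be empty whatever its thresholds.

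**The case against.** The case for leaving the table alone is substantial.

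- Lower elevations are not hidden. The shift tables, the visit-wise maxima and the grade 3/4 listing all report values below 5 x ULN. Under Protocol Section 8.3.1, a laboratory abnormality that causes symptoms, needs intervention, interrupts treatment or is judged clinically significant is also an adverse event, tabulated under SAP Section 6.6.1. This stands, and it is why extra lower single-test rows would add little.
- Counting at the protocol's own limit is coherent, and the SAP claims no wider purpose for the table. This also stands.
- Neither document sets a joint criterion or requires one, so no stated commitment is breached. The clinical case for a joint row and any cut-offs below 5 x ULN come from outside the documents. This stands, and the cut-offs need the sponsor's confirmation.
- The 5 percentage points are what any single uncounted event would give in 20 patients. The documents give no likelihood of such a case.

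A reader might go further and infer that the study report would conclude there were no liver elevations, or that a coincident rise could never be seen. The documents support neither. The first ignores the other displays in the same section. The second ignores the dated listing, and the SAP's mention of laboratory data listings from which a case might be pieced together by hand. What none of these displays supplies is a summary of joint elevation.

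**Conclusion.** The point holds in a limited form. SAP Section 6.6.4 counts the three tests separately and only above 5 x ULN, and no planned summary shows whether transaminase and bilirubin elevations occurred together in one patient. The certain gap is the missing joint summary, together with any joint elevation in which no value reaches grade 3, which no specified listing would pick out.

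One missed man is 1/20 rather than 0/20. This sizes a single case; it does not forecast one. Calling 5 x ULN a stopping limit is shorthand, because the protocol's rule is conditional.

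The conclusion assumes that the table has only the three rows visible. The text available has a blank row above AST, probably formatting, though a lost row cannot be fully excluded. Severity is minor: neither the primary nor the secondary endpoint is affected.

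**What to change.** Change the reporting only; the discontinuation rule in Protocol Section 5.3 is not touched.

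1. Add one row to the liver table: patients with ALT or AST elevation and total bilirubin elevation on the same sample date, at pre-specified cut-offs below 5 x ULN. For example, ALT or AST >3 x ULN with bilirubin >2 x ULN could serve as a reporting assumption for the sponsor to confirm.
2. Add a by-patient listing of those cases with sample dates, all three tests, alkaline phosphatase and a flag for Gilbert's disease.
3. Reconcile the central-laboratory restriction in SAP Section 6.6.4 with Protocol Sections 8.4 and 12, so that the table draws on the local results actually collected.

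The cost is an edit to the SAP text and table shell. ALT, AST, total bilirubin and alkaline phosphatase are already in the same chemistry panel (Protocol Table 12), so no new test or visit is needed. The downside is a few more rows, and some mild or Gilbert-related values on display.
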